#### *Medications*

20. Any medications that, in the opinion of the Investigator, may contribute to cognitive impairment, put the subject at higher risk for AEs, or impair the subject's ability to perform cognitive testing or complete study procedures.
21. Use of allowed chronic medications at doses that have not been stable for at least 4 weeks prior to Screening Visit 1 and during Screening up to Study Day 1, or use of AD medications (including but not limited to donepezil, rivastigmine, galantamine, tacrine, and memantine) at doses that have not been stable for at least 8 weeks prior to Screening Visit 1 and during Screening up to Study Day 1.
22. Use of medications with platelet anti-aggregant or anti-coagulant properties (the use of aspirin at a prophylactic dose [ $\leq 325$  mg daily] is allowed).
23. Use of illicit narcotic medication.
24. Vaccinations within 10 days prior to randomization (Day 1).
25. Participation in any active immunotherapy study targeting A $\beta$  unless documentation of receipt of placebo is available.
26. Participation in any passive immunotherapy study targeting A $\beta$  within 12 months of Screening unless documentation of receipt of placebo is available.
27. Participation in any study with purported disease-modifying effect in AD within 12 months prior to Screening unless documentation of receipt of placebo is available. Subjects who developed ARIA-E during a previous disease-modifying trial should be excluded.
28. Participation in a previous study with aducanumab (subject is eligible if he/she did not receive active aducanumab).

#### *Study Procedures*

29. Contraindications to having a brain MRI (e.g., pacemaker, MRI-incompatible aneurysm clips, artificial heart valves, or other metal foreign body; claustrophobia that cannot be medically managed).
30. Contraindication to having a PET scan (e.g., inability to lie flat or still for the duration of the scan) or intolerance to previous PET scans (i.e., previous hypersensitivity reactions to any PET ligand or imaging agent, failure to participate in and comply with previous PET scans).
31. A negative PET scan result with any amyloid-targeting ligand within 6 months prior to Screening.
32. Have had or plan exposure to experimental radiation within 12 months prior to Screening such that radiodosimetry limits would be exceeded by participating in this study.

CONFIDENTIAL

The information contained herein may not be used, disclosed, or published without the written consent of  
Biogen MA Inc.

33. For subjects who consent to LP, any contraindications to having a LP (e.g., platelet count <100,000/ $\mu$ L, lumbar spine deformity). Any symptoms caused by or related to the optional LP during Screening must be resolved prior to randomization (Day 1). Subjects may still participate in the overall study even if participation in the optional LP portion is contraindicated.

*Others*

34. Female subjects who are pregnant or currently breastfeeding.
35. Previous participation in this study. Subjects who fail Screening will be permitted to be rescreened once at the Sponsor's discretion, except those who fail due to PET, MMSE, CDR global score >0.5, hepatitis B or C, or abnormal MRI findings. (Subjects who fail Screening due to a CDR global score of 0 may be rescreened; such subjects will be allowed to repeat the screening CDR assessment after 6 months.)
36. Subject currently living in an organized care facility with extensive intervention and/or support of daily living activities.
37. Blood donation ( $\geq$  1 unit) within 1 month prior to Screening.
38. Inability to comply with study requirements.
39. Other unspecified reasons that, in the opinion of the Investigator or Biogen, make the subject unsuitable for enrollment.

### **8.3. Inclusion Criteria for Long-Term Extension Period**

To be eligible to participate in the LTE period, subjects must meet the following eligibility criteria at Week 78:

1. Subject must have completed the placebo-controlled period of the study including the Week 78 Visit. Subject must have taken at least 14 doses and not have missed more than 4 consecutive doses, except for subjects whose dose was suspended due to ARIA (See Section 7.2.1). Subjects who do not meet these criteria may enter the LTE period only with Sponsor's approval.
2. The subject (or the subject's legally authorized representative) has the ability to understand the purpose and risks of the study and provide signed and dated informed consent (or assent) and authorization to use confidential health information in accordance with national and local subject privacy regulations.
3. Female subjects of childbearing potential and male subjects must practice highly effective contraception during the study and for 24 weeks after their last dose of study treatment.
4. Apart from a clinical diagnosis of AD, the subject must be in good health as determined by the Investigator, based on medical history.
5. Must have the ability to comply with procedures for protocol-related tests.

CONFIDENTIAL

The information contained herein may not be used, disclosed, or published without the written consent of Biogen MA Inc.

6. Has one informant/care partner who, in the Investigator's opinion, has frequent and sufficient contact with the subject as to be able to provide accurate information about the subject's cognitive and functional abilities. The informant/care partner must minimally be available by phone to provide information to the Investigator and study staff about the subject and agrees to attend in person clinic visits that require partner input for scale completion. An informant/care partner should be available for the duration of the study, and the use of the same informant/care partner for the duration of the study is encouraged.

#### **8.4. Exclusion Criteria for Long-Term Extension Period**

Subjects will be excluded from entering the LTE period if at Week 78 they have:

1. Any medical or psychiatric contraindication or clinically significant abnormality that, in the opinion of the Investigator, will substantially increase the risk associated with the subject's participation in and completion of the study.

CONFIDENTIAL

The information contained herein may not be used, disclosed, or published without the written consent of  
Biogen MA Inc.

## **9. ENROLLMENT, REGISTRATION, AND RANDOMIZATION**

### **9.1. Screening and Enrollment**

Subjects (or their legally authorized representative, where applicable) must provide informed consent before any screening tests are performed (see Section 17.3). During Screening, subjects can complete the neurocognitive scales (CDR, MMSE and RBANS) and ApoE genotyping to determine study eligibility under a separate, optional initial consent process. If the subject meets inclusion criteria for these 3 scales the full consent process must be completed prior to the administration of further screening assessments. Subjects may also proceed directly to the full consent process which would allow the administration of all screening assessments. When a subject signs the full informed consent form (ICF), that subject is considered to be enrolled in the study. ApoE genotyping may be performed at Visit 1 prior to other screening assessments.

Participating study sites are required to document all screened candidates initially considered for inclusion in this study. It is recommended that all screening procedures be completed within 60 days; however, the overall screening period may be extended up to 90 days in the event of logistical issues related to PET scans and is subject to Sponsor approval. If a subject is excluded from the study, the reasons for exclusion will be documented in the subject's source documents and on the screening log. The total study duration for each subject participating only in the placebo-controlled period will be approximately 102 weeks (approximately an 8-week screening period, 76 weeks of placebo or aducanumab dosing, and 18 weeks of FU).

### **9.2. Randomization and Registration of Subjects**

Subjects will be registered at the Screening Visit and randomized only after all baseline assessments have been completed and the Investigator has verified that the subjects are eligible per criteria in Sections 8.1 and 8.2. No subject may begin treatment prior to assignment of a unique identification number (registration) and randomization. Any subject identification numbers or randomization schedule assignments that are assigned will not be reused even if the subject does not receive treatment. Rescreened subjects will be assigned a new number.

Subjects will be randomized to receive aducanumab low dose:aducanumab high dose:placebo in a 1:1:1 ratio. The randomization will be stratified by site and ApoE  $\epsilon$ 4 status (carrier or non-carrier). Subjects randomized to placebo at the start of the placebo-controlled period will also be randomized to receive dose-blinded aducanumab (low dose:high dose, 1:1 ratio) for the LTE period and randomization will be stratified by subject ApoE  $\epsilon$ 4 carrier status. Treatment group assignments for the placebo-controlled period and the LTE period will be assigned at Study Day 1. Enrollment will be monitored, via the IRT, such that the population of subjects with mild AD represents a small percentage of the total enrolled in the trial. Subjects who withdraw from the study may not be replaced.

Refer to the Study Reference Guide for details on registration and randomization.

CONFIDENTIAL

The information contained herein may not be used, disclosed, or published without the written consent of Biogen MA Inc.

### 9.3. Blinding Procedures

This study consists of a randomized, double-blind, placebo-controlled period, followed by a dose-blinded LTE period with all subjects receiving aducanumab.

For the double-blinded placebo-controlled period, all study staff who conduct subject assessments will be blinded to the subject treatment assignments. The rating HCPs should remain blinded to treatment assignment as well as subject care management and only have access to the information necessary to carry out their responsibilities as detailed in Section 4.3.1. As a placebo match is not provided for the study, unblinded pharmacy staff are required to manage all aspects of study treatment receipt, dispensing, and preparation. To maintain the study blind, it is imperative that subject treatment assignments are not shared with the subjects, their families, or any member of the blinded study team, either at the study site or at Biogen or its representatives, except the unblinded pharmacist (or designee), the unblinded pharmacy monitor, and the unblinded [REDACTED] or Biogen safety staff.

For the LTE period, the dose information must remain restricted. The rating and treating HCP should remain blinded to treatment assignment and only have access to the information necessary to carry out their responsibilities as detailed in Section 4.3.1. To maintain the study blind, it is imperative that dose information is not shared with the subjects, their families, or any member of the blinded study team, either at the study site or at Biogen or its representatives, except the unblinded pharmacist (or designee), the unblinded pharmacy monitor, and the unblinded [REDACTED] or Biogen safety staff.

CONFIDENTIAL

The information contained herein may not be used, disclosed, or published without the written consent of Biogen MA Inc.

## 10. DISCONTINUATION OF STUDY TREATMENT AND/OR WITHDRAWAL OF SUBJECTS FROM THE STUDY

### 10.1. Discontinuation of Study Treatment

A subject *must* permanently discontinue study treatment for any of the following reasons:

- The subject develops any of the following:
  - ARIA-E accompanied by serious clinical symptoms except for “other medically important event” as defined in [Table 13](#).
  - Symptomatic ARIA-H (microhemorrhages) with serious clinical symptoms except for “other medically important event” as defined in [Table 14](#).
  - Symptomatic ARIA-H (superficial siderosis) with or serious clinical symptoms except for “other medically important event” as defined in [Table 15](#).
  - ARIA-H with  $\geq 10$  microhemorrhages and/or  $>2$  focal areas of superficial siderosis.
  - Any new incident macrohemorrhage (defined as  $>1$  cm in diameter on T2\* sequence).

See Section 7.2.1 for full details regarding discontinuation and dose reduction due to ARIA-E or ARIA-H.

- The subject becomes pregnant. Study treatment must be discontinued immediately and pregnancy must be reported according to the instructions in Section 15.4.1.
- The subject withdraws consent to continue study treatment.
- The subject experiences a medical emergency that necessitates permanent discontinuation of study treatment or unblinding of the subject's treatment assignment.
- The subject experiences an AE that does not resolve or requires continued treatment that meets exclusionary criteria (see Section 11.5.1.2).
- The subject experiences a severe infusion reaction.
- At the discretion of the Investigator for medical reasons.
- At the discretion of the Investigator or Sponsor for noncompliance.

The reason for discontinuation of study treatment must be recorded in the subject's case report form (CRF).

A subject who discontinues treatment is to remain in the study, attend a FU Visit 18 weeks after the final dose, and immediately continue protocol-required tests and assessments at a subset of the clinic visits (see [Table 10](#) and [Table 11](#)) until the end of the study per the schedule of events or until the subject withdraws consent.

CONFIDENTIAL

The information contained herein may not be used, disclosed, or published without the written consent of  
Biogen MA Inc.

## 10.2. Withdrawal of Subjects From Study

Subjects must be withdrawn from the study for any one of the following reasons:

- The subject withdraws consent.
- The subject is unwilling or unable to comply with the protocol.
- At the discretion of the Investigator or Sponsor.

Note: A subject who discontinues study treatment will not be automatically withdrawn from the study, regardless of the number of doses missed. The subject is to remain in the study, and continue with a FU Visit 18 weeks after the final dose, and protocol-required tests and assessments at a subset of the clinic visits (see [Table 10](#) and [Table 11](#)) until the end of the study or until the subject withdraws consent.

The reason for the subject's withdrawal from the study must be recorded in the subject's CRF.

Subjects who are withdrawn from the study after receiving  $\geq 1$  doses of study treatment should complete the EOT Visit after the reason for withdrawal is identified. For such subjects, efficacy assessments specified at the EOT Visit are not required if the subject discontinues treatment within 3 months of the previous efficacy assessment visit and no significant changes in cognitive status are suspected by the Investigator; The site should notify the sponsor in such cases. Subjects who are withdrawn from the study are also to return to the site for a FU Visit 18 weeks after receiving their last dose of study treatment.

CONFIDENTIAL

The information contained herein may not be used, disclosed, or published without the written consent of  
Biogen MA Inc.

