SAE Reporting	Monitor and record continuously throughout the study.															

Ab = antibody; AD = Alzheimer's disease; AE = adverse event; ADAS-Cog 13 = Alzheimer's Disease Assessment Scale Cognitive Subscale (13 items); ADCS-ADL-MCI = Alzheimer's Disease Cooperative Study Activities of Daily Living Inventory (Mild Cognitive Impairment version); ARIA = amyloid-related imaging abnormalities; ARIA-E = amyloid-related imaging abnormality-edema; ARIA-H = amyloid-related imaging abnormality hemorrhage or superficial siderosis; [REDACTED]; CDR = Clinical Dementia Rating scale; [REDACTED]; C-SSRS = Columbia Suicide Severity Rating Scale; DCT = discontinue treatment; ECG = electrocardiogram; EOT = end of treatment; [REDACTED]; EQ-5D (IR-S) = EQ-5D, informant reported on subject; FU = follow-up; LTE = long-term extension; MMSE = Mini Mental State Examination; MOCA = Montreal Cognitive Assessment; MRI = magnetic resonance imaging; NPI-10 = Neuropsychiatric Inventory-10; PBMC = peripheral blood mononuclear cells; PET = positron emission tomography; PK = pharmacokinetic; [REDACTED]; SAE = serious adverse event; UV = unscheduled visit; wks = weeks.

 Subjects who complete the LTE period are to return to the site for a safety FU Visit at Week 354. Subjects who discontinue treatment or withdraw from the study early are to have a safety FU Visit at 18 weeks after their final dose.

 Subjects who discontinue treatment prematurely are to remain in the study, attend a FU Visit 18 weeks after the final dose, and immediately continue protocol-required tests and assessments continue protocol-required tests and assessments at a subset of the clinic visits (see Table 11) until the end of the study per the schedule of events. (It is possible that a clinic visit will occur before the FU Visit.) If the FU Visit will occur within 2 weeks of a scheduled clinic visit, then the FU Visit can be combined with the scheduled visit and all assessments required for both visits performed at this single visit. Subjects who withdraw from study prematurely are to return to the site for an EOT Visit. For subjects who discontinue treatment early, efficacy assessments specified at the EOT visit are not required if the subject discontinues treatment within 3 months of the previous efficacy assessment visit and no significant changes in cognitive status are suspected by the Investigator. The site should notify the Sponsor in such cases.

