-  Subjects who withdraw from study prematurely are to return to the site for an EOT Visit; for such subjects, efficacy assessments specified at the EOT Visit are not required if the subject discontinues treatment within 3 months of the previous efficacy assessment visit and no significant changes in cognitive status are suspected by the Investigator. The site should notify the Sponsor in such cases.
-  For the frequency of required brain MRI and MOCA assessments, and PK, biomarker, and PBMC sample collection for subjects who develop ARIA-E and/or ARIA-H, see Section 7.2.1.1 to Section 7.2.1.5. This includes PK, biomarker, and PBMC sample collection at the first unscheduled visit for ARIA monitoring per episode only. For the frequency of brain MRI and MOCA assessments following resolution of ARIA and resumption of dosing, see Section 7.2.1.6. For management of recurrent ARIA, see Section 7.2.1.7.
-  Only for subjects entering the long-term extension period.
-  Sample may be collected within  $\pm 2$  days of the MRI visit at the same time as sample collection for aducanumab concentration.
-  One sample will be collected within  $\pm 2$  days of the MRI visit. Exact collection date and time will be captured for all PK blood samples on a specified case report form.
-  Arterial spin labeling MRI and task-free functional MRI will be performed only at a subset of sites.
-  Only for subjects who participate in the amyloid PET substudy. Amyloid PET may be scheduled within a window of  $\pm 7$  days.

CONFIDENTIAL

The information contained herein may not be used, disclosed, or published without the written consent of Biogen MA Inc.

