### 4.3. Additional Information

#### 4.3.1. Site Personnel

A minimum of 3 separate health care professionals (HCPs) are required:

1. A treating HCP (the Principal Investigator [PI] or Sub-investigator may serve as a treating HCP) who is responsible for the following:
  - Administration of Montreal Cognitive Assessment (MOCA) at Day 1, Week 80, and during management of amyloid-related imaging abnormalities (ARIA) cases.
  - Management of routine neurological care of the subject.
  - Assessment (including assignment of causality) and treatment of adverse events (AEs).
  - Review of selected hematology and blood chemistry results from the central laboratory to assess if the subject's study treatment should be temporarily withheld or permanently discontinued according to the criteria detailed in Section 10.1.
2. An independent rating HCP (designated by the PI of the site) who is responsible for administering the Clinical Dementia Rating (CDR)
3. A second independent rating HCP (designated by the PI of the site) who will administer the Alzheimer's Disease Assessment Scale-Cognitive Subscale (13 items) [ADAS-Cog 13], Alzheimer's Disease Cooperative Study-Activities of Daily Living Inventory (Mild Cognitive Impairment version) [ADCS-ADL-MCI], and the Mini-Mental State Examination (MMSE)

The 2 independent rating HCPs must not be involved with any other aspect of subject care and management and must remain blinded to AEs, concomitant therapy, laboratory data, imaging data, or any other data that have the potential of revealing the treatment assignment. The 2 independent rating HCPs must not share any information about subjects. PIs cannot serve as rating HCPs. The treating HCPs must not discuss AEs (e.g., ARIA) with the independent rating HCPs.

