## 7.2. Study Specifics

### 7.2.1. Dose Suspension, Modification, or Termination for ARIA Events

#### *Discontinuation of Dosing for a Given Subject*

The central MRI reading center will report incident cases of ARIA-E and ARIA-H to both the Sponsor and the PI within a specified time after observing the finding on MRI per the imaging manual procedures. All cases of ARIA will be reviewed by the Sponsor and the PI; decisions on dosing continuation, interruption, or discontinuation will be based on clinical symptoms, and the MRI information provided by the central reader. IDMC notification rules will be outlined in the IDMC charter. Guidelines on the management and disposition of ARIA-E and ARIA-H cases (including the criteria to be met for the continuation, suspension/resumption, permanent discontinuation of dosing due to ARIA, resumption of dosing after dose suspension due to ARIA [including rules for titrating up to the assigned dose], and management of recurrent ARIA) are provided in the following subsections. Dosing may also be terminated at the discretion of the Sponsor for medical reasons. See Section 10.1 for the full list of criteria for discontinuing study treatment.

CONFIDENTIAL

The information contained herein may not be used, disclosed, or published without the written consent of Biogen MA Inc.

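### Within 3 months of an efficacy visit, recording a withdrawing subject's exit CDR-SB depends on whether the Investigator suspects cognitive change

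*Protocol*

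**What the plan says.** Section 10.2 (Version 6.0) asks subjects withdrawn after at least one dose to complete the EOT Visit, and then relaxes this: "efficacy assessments specified at the EOT Visit are not required if the subject discontinues treatment" and does so "within 3 months of the previous efficacy assessment visit and no significant changes in cognitive status are suspected by the Investigator". Both conditions must hold, and the site notifies the Sponsor. The EOT footnotes of Tables 2, 3, 10 and 11 repeat the rule for subjects who withdraw; Table 10 reads "efficacy assessments specified at the EOT Visit are not required if the subject discontinues treatment within 3 months of the previous efficacy assessment visit". The Table 9 footnote (LTE, from Week 288) addresses a different group: "For subjects who discontinue treatment early, efficacy assessments specified at the EOT visit are not required".

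**Who decides.** Section 7.2.1 states "The central MRI reading center will report incident cases of ARIA-E and ARIA-H to both the Sponsor and the PI". Section 4.3.1 gives the CDR to an independent rater shielded from adverse events and imaging, and adds "PIs cannot serve as rating HCPs". The PI or a sub-investigator may be the treating professional who handles adverse events. Section 7.1 keeps Investigators blinded to assignment.

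**What else is collected.** Subjects who only stop treatment stay in the study, with CDR at Weeks 26, 50 and 78 (Table 10). Withdrawn subjects have a FU Visit 18 weeks after the last dose, for which Table 2 lists CDR, MMSE, ADAS-Cog 13 and ADCS-ADL-MCI. Section 10.2 expects them to attend; Section 7.3.3 only encourages it.

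**Analysis.** Section 16.2.2.4 specifies an MMRM on change from baseline in CDR-SB in the ITT population.

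**The concern.** An MMRM gives valid estimates if, given the data observed, missingness does not depend on the missing value. The Investigator's suspicion of change since the last rating is a judgement about that missing value, and it is not in the model. No analysis plan can recover a score that was never taken, so this is not a matter left to the SAP.

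The protocol shields the CDR rating from ARIA but not the decision whether to rate. Section 5.1.2 reports that ARIA depends on dose: among carriers in the earlier multiple-dose study, ARIA-E occurred in 35% with titration to 10 mg/kg, 43% at fixed 6 mg/kg and 55% at fixed 10 mg/kg. If knowing of ARIA changes how readily decline is suspected, exit recording could differ between arms.

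A second fault is the clock. The rule governs withdrawal from the study, but its 3 months end when treatment stops.

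**Working it through.** **1. The plan's own figure.** Section 16.8: difference 0.5, SD 1.92, two-sided 0.05, 90% power, 30% drop-out. n = 2 × 1.92² × (1.960 + 1.282)² / 0.5² = 310 evaluable per arm; 310 / 0.70 = 443, against 450 stated. It reproduces. The target is now 535 per arm.

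**2. Share of withdrawals inside the window.** Assumptions: 3 months is 13 weeks, withdrawals are uniform over 78 weeks, and treatment stops at withdrawal.

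| Interval (weeks) | Waivable | Share |
|---|---|---|
| 0 to 26 | 13 of 26 | 50% |
| 26 to 50 | 13 of 24 | 54% |
| 50 to 78 | 13 of 28 | 46% |

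- All three intervals: 39/78 = 50%.
- Baseline rating 60 days (8.6 weeks) before Day 1: (4.4 + 13 + 13)/78 = 39%.
- Only the windows after Weeks 26 and 50: 26/78 = 33%.

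**3. Subjects affected, as a ceiling.** 0.30 × 0.333 = 10% and 0.30 × 0.50 = 15% of subjects, or 54 to 80 per arm of 535. This treats the whole 30% as study withdrawal, and it includes suspected decliners, who are rated.

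**4. Illustrative bias at Week 78.** Suppose the exit score is mapped to Week 78, the rule withholds the best share q of in-window exit scores in one arm, and every score is recorded in the other. Then

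bias ≈ p × w × SD × √(1 − ρ²) × φ(z_q)

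with p the share withdrawn, w = 0.5 the share in the window, ρ the correlation between visits and φ the normal density.

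- Largest case (p = 0.30, ρ = 0.5, q = 0.5): 0.15 × 1.92 × 0.866 × 0.399 = 0.10, or 20% of 0.5.
- Smallest case (p = 0.10, ρ = 0.8, q = 0.8): 0.05 × 1.92 × 0.600 × 0.280 = 0.016, or 3% of 0.5.

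A two-visit maximum-likelihood simulation under no treatment effect, at ρ = 0.7, gave 0.02 to 0.09. With the same rule acting equally in both arms, the difference was about 0 (within 0.003). The arm to which the rule applies looks worse than it is.

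**5. The clock.** If treatment stops at withdrawal, the latest waivable exit is about Week 50 + 13 = Week 63, 15 weeks before the endpoint. Read literally, a subject who stops treatment at Week 28 (2 weeks after the Week 26 rating) and withdraws at Week 48 also qualifies, 22 weeks after the last rating. Table 10 has no efficacy visit between Weeks 26 and 50.

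**The case against.** The case for leaving the rule alone has weight.

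- **It is a limited waiver.** Beyond 3 months the battery is required, and inside the window it is optional, not forbidden. Sparing someone rated recently is a defensible aim, and a subject who has withdrawn consent cannot be compelled. This stands, but it supports a fixed time limit, not a condition on suspected cognition.
- **There is a back-up.** The FU Visit carries the CDR with no suspicion condition. This stands in part, because Section 7.3.3 only encourages attendance.
- **Exit scores may hardly enter the model.** The midpoints between efficacy visits are Weeks 38 and 64, and the waiver windows end at Weeks 39 and 63. If scores go to the nearest visit (an assumption, since the mapping belongs to the SAP), most waived scores would fall to a visit already rated. The exceptions are exits before Week 26 and late withdrawals under the literal clock. This stands and is a main reason to call the effect small.

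A reader might also infer more than the documents support:

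- **That the outcome rater knows of ARIA.** The CDR rater is separate and shielded; the Investigator decides only whether to measure.
- **That subjects stopped for ARIA lose their assessments.** They stay on scheduled efficacy ratings at a subset of visits; in the placebo-controlled period the waiver concerns study withdrawal only.
- **That arm imbalance is established.** The protocol reports dose dependence but gives no placebo ARIA rate here, no recording rates by arm, and nothing on how knowledge of ARIA shifts suspicion.
- **That the MMRM carries the last value forward to Week 78.** It uses all observed visit values; a selectively missing score matters through the missing-at-random assumption.

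**Conclusion.** The concern holds in a limited form. Within the 3-month window, recording of exit CDR-SB depends on the suspected current outcome, as judged by an Investigator who is blinded to assignment but told of ARIA. That can violate missing at random and could do so differently by arm. The 3-month clock is tied to the wrong event.

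The size is probably small: 0 to 0.10 points against 0.5. The upper end requires 30% study withdrawal, half of it in the window, selective recording in one arm only, and exit scores mapped to Week 78. The documents establish none of these. The count of 54 to 80 per arm is a ceiling on who could be affected, not a forecast of lost scores. The Table 9 wording cannot touch the Week 78 endpoint. The change is worth making because it is cheap and the missing scores cannot be recovered later; it is not grounds to distrust the primary analysis.

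**What to change.** - In Section 10.2 and the EOT footnotes of Tables 2, 3, 10 and 11, delete the condition on the Investigator's suspicion. Request at least CDR and MMSE at the EOT Visit of every withdrawing subject who is willing.
- If burden must be limited, keep only a fixed waiver based on the time from the last efficacy assessment to the date of withdrawal.
- Reconcile the Table 9 footnote, which words the waiver for treatment discontinuers in the LTE, with Table 11 and Section 10.2, which keep those subjects on scheduled assessments at a subset of visits.

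The visit, raters and scales already exist. The cost is one battery for at most about 10-15% of subjects, with some added burden on people who are leaving. Sample size and alpha do not change.
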